Official Title: Evaluation of Artificial Intelligence for Adenoma Detection in Water Exchange Colonoscopy: the WEAID Randomized Controlled Trial (Water Exchange With Artificial Intelligence-assisted Detection)

NCT number: 06173258

Date of Document: Oct 1, 2023.

Introduction

Adenoma detection rate (ADR) and adenoma per colonoscopy (APC) are crucial predictors for postcolonoscopy colorectal cancer (CRC). Water Exchange (WE) colonoscopy maximizes bowel cleanliness during insertion and has demonstrated superiority in increasing ADR and APC as compared to air insufflation.

Artificial intelligence (AI) lesion computer-aided detection (CADe) devices present promising tools for colonoscopies. Meta-Analysis reveals that AI generates an average ADR gain of 8% and an average APC gain of 0.20 in air-insufflated colonoscopy.

Recent research confirmed that the addition of AI to WE elevated ADR, and the application of WE to AI reduced false positive (FP) instances per colonoscopy, as evidenced by the analysis of pre-recorded video in a randomized controlled trial (RCT) comparing WE and air insufflation. Pilot retrospective data involving 715 patients (367 in the AI group, 348 in the control group) from Italy and Taiwan, with a mean age of 59.6 years (51.5% men) showed that WE with AI demonstrated numerical APC enhancement (1.31 ± 1.80 vs. 1.14 ± 1.38 , $P = 0.152$) and significantly increased the detection rate of proximal sessile serrated lesion (SSL) (5.2% vs. 2.3%, $P = 0.044$) in comparison to WE alone (Tables 1 and 2) (Cheng CL et al. Gastrointest Endosc 2024;99:AB17–18).

Table 1. Per-patient ADR and APC in water exchange (WE) with CADe pilot study

Detection of adenomas	WE without CADe (n=348)	WE with CADe (n=367)	P value
Overall ADR, n (%)	203 (58.3)	207 (56.4)	*0.602
Right ADR, n (%)	106 (30.5)	107 (29.2)	*0.703
Proximal ADR, n (%)	132 (37.9)	149 (40.6)	*0.465
Overall APC, mean (SD)	1.14 (1.38)	1.31 (1.80)	[†] 0.152

*Fisher exact test. [†]Student's *t* test

Table 2. Detection of sessile serrated lesions in WE with CADe pilot study

Detection of SSLs	WE without CADe (n=348)	WE with CADe (n=367)	P value
SSL detection rate			
Overall SSL detection rate, n (%)	10/348 (2.9)	21/367 (5.7)	*0.062
Right SSL detection rate, n (%)	7 (2.0)	14 (3.8)	*0.153
Proximal SSL detection rate, n (%)	8 (2.3)	19 (5.2)	*0.044
Detected SSL per colonoscopy			
Right SSL per colonoscopy, mean (SD)	0.02 (0.17)	0.06 (0.36)	[†] 0.062

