Randomization: Enrolled patients will be randomized in a 1:1 ratio to either the WE with AI-assisted colonoscopy (study group) or WE colonoscopy alone (control group). Randomization will be carried out by computer-generated sequences using a block design (four participants per block). Stratification will be based on study sites, colonoscopists, and colonoscopy indications (primary screening, surveillance, and positive FIT or gFOBT).

Artificial intelligence: Commercially available AI system (CAD-EYE, Fujifilm, EU and Taiwan; Endo-AID, Olympus, EU and Taiwan) will be employed. During AI-assisted procedures, the AI will be activated during the withdrawal phase of the procedure, providing a bounding box as output any time a lesion that is suspected to be a polyp is recognized by the CADe device. At each center, expertise in AI was already developed prior to the start of the study.

Data collection: To capture all study data comprehensively, a case record form will be employed. This form, available in written format, will document various aspects of the study, including enrollment procedures, randomization, colonoscopy details, histological results, and safety information. Study investigators and their teams are responsible for completing all sections of a pre-built Microsoft Excel worksheet.

Colonoscopy procedure: Bowel preparation regimens will align with established standard practices at each individual site. The study procedures employ standard high-definition colonoscopy video processors with integrated AI systems. In both arms of the study, insertion and withdrawal of the colonoscope will be executed by the same colonoscopist. The evaluation and grading of bowel preparation quality will

be carried out using the Boston Bowel Preparation Scale scoring system.

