During the insertion phase of WE colonoscopy, the air pump will be turned off, while the colon will be irrigated with water using a flushing pump. The WE approach involves the simultaneous infusion of water to facilitate luminal expansion and suction of unclean water during insertion. Any encountered air pockets will be aspirated to ensure optimal WE maneuver in salvage cleaning. Upon reaching the cecum, where most of the water is suctioned to collapse the cecal lumen, the air pump will be opened. All investigators will be asked to adhere to WE technique confirmation of nearly equivalent volumes of water infused and suctioned upon cecal arrival. During the withdrawal phase, air or CO₂ will be insufflated in both arms.

Withdrawal from the cecum will begin in the left lateral position. Similar withdrawal techniques with adequate luminal distention and comprehensive examination will be emphasized. Adhering to prevailing guidelines set by the American and European Societies of Gastrointestinal Endoscopy, a minimum of 6 minutes of clean withdrawal time will be maintained for all colonoscopies across both arms.

During the withdrawal phase, an exhaustive polyp search and subsequent resection will be performed in both study arms. Comprehensive records will be maintained for all detected polyps, capturing size (assessed in comparison with open forceps or snare), precise location, and morphology (classified according to the Paris classification).

False positives of AI: False positive (FP) activation is defined as the identification by AI systems of an area during the withdrawal phase that is not deemed to be a colorectal lesion after re-examination by the colonoscopist. Real-time flagging of FP activation is recorded by investigators and study staff. The NOISE classification will be

used to categorize the causes of FP activations.

Study outcomes: The primary outcome is APC, calculated as the total number of adenomas detected divided by the total number of colonoscopies performed. Secondary outcomes encompass 1) overall ADR, 2) ADR and APC in the right and proximal colon, 3) SSL detection rates, 4) mean number of non-neoplastic lesions resected per colonoscopy, 5) real-time number of FPs per colonoscopy, and 6) procedural times (e.g., insertion time, withdrawal time, and total procedural time).

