Sample size calculation: For group comparison, the sample size was determined assuming that the APC of the control group is 0.9. A clinically significant relative increase of 25% in APC was considered. With a two-sided significance level of 5% and 80% power, 376 patients will be required per group (752 randomized patients). Accounting for a 10% overall dropout rate, enrollment of at least 836 patients is planned.

Statistical analysis: Categorical variables are presented as frequencies and percentages and continuous variables as means with standard deviations. The analysis will follow the intention-to-treat approach. Student's *t*-test will be used for continuous variables and chi-square test will be used for categorical variables. Poisson regression will be used to calculate incident rate ratios comparing the APC between the two arms, adjusting for age, sex, body mass index, smoking history, CADe system, and bowel preparation quality. A planned interim analysis will be conducted after the recruitment of approximately 70% of the planned enrollment to determine whether early termination of the study is appropriate to minimize the number of patients in the control group given the less effective, or clearly inferior

treatment. All statistical analyses will be performed using Python version 3.10 (SciPy Library). A *P* value < 0.05 is considered significant.

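### ADR is tested unadjusted although the baseline covariates for the APC model are already needed, so a small and nearly free gain in precision is given up

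*Combined protocol and SAP*

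**What the plan says.** The Statistical analysis section of the combined protocol and SAP sets two default tests, Student's t for continuous variables and, for the rest, "chi-square test will be used for categorical variables". It then gives one adjusted model, a Poisson regression "comparing the APC between the two arms, adjusting for age, sex, body mass index, smoking history, CADe system, and bowel preparation quality".

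The Study outcomes section makes APC primary and continues: "Secondary outcomes encompass 1) overall ADR, 2) ADR and APC in the right and proximal colon, 3) SSL detection rates". Non-neoplastic resections, false positives and procedure times follow. No adjusted model is named for ADR at any location, so ADR takes the default chi-square test. The Poisson sentence does not say whether it covers overall APC only, or right and proximal APC as well.

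The Data collection section does not list age, sex, BMI or smoking by name. Their collection is implied by the APC model.

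**The concern.** ADR is the same adenoma count cut at one or more. If age, sex, BMI and smoking are worth adjusting for when adenomas are counted, the documents give no reason to ignore them when the count is dichotomised. The Introduction names ADR beside APC as a key predictor of post-colonoscopy cancer, and overall ADR is the first secondary outcome.

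Two things are at stake. The ADR comparison is less precise than the collected data allow. And a chance imbalance in, say, age would be taken out of the adjusted APC estimate but not out of ADR, so the two could differ for a reason unrelated to AI. In the pilot (Table 1) they already moved in opposite directions: APC was "1.31 ± 1.80 vs. 1.14 ± 1.38" with and without AI, while ADR was 56.4% and 58.3%.

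**Working it through.** **The plan's own figure.** The only sample size is for APC: 376 per group, with control APC 0.9, a 25% increase (to 1.125, difference 0.225), two-sided 5% and 80% power. Two Poisson rates give (1.960 + 0.842)² × (0.9 + 1.125) / 0.225² = 7.849 × 2.025 / 0.050625 = 314 per group, so the stated inputs alone do not return 376. An unstated SD of 1.10 does: 2 × 7.849 × 1.10² / 0.050625 = 375.2, rounded up to 376. The dropout step reproduces: 752 / 0.9 = 836. The APC calculation is a separate matter; here 376 is only the number analysed per arm. The plan gives no power for ADR.

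**Inputs for ADR**
- Control ADR 58.3% (Table 1, water exchange without CADe).
- AI-arm ADR 66.3%, that is, plus 8 points. The Introduction reports this gain for air-insufflated colonoscopy, so for water exchange it is an assumption.
- Share of ADR variance explained by the four covariates (R²): not in the documents; assumed 2% to 9%.

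**Unadjusted power.** Pooled rate 0.623.
- SE under no difference: √(2 × 0.623 × 0.377 / 376) = 0.03535.
- SE under the alternative: √((0.583 × 0.417 + 0.663 × 0.337) / 376) = 0.03523.
- Power: Φ((0.08 − 1.96 × 0.03535) / 0.03523) = Φ(0.304) = 62.0%.

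**Adjusted power, by formula.** Adjustment acts roughly like raising n to 376 / (1 − R²).

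| Assumed R² | Effective n per arm | Power |
|---|---|---|
| 0 | 376 | 62.0% |
| 0.02 | 383.7 | 62.8% |
| 0.05 | 395.8 | 64.2% |
| 0.09 | 413.2 | 66.1% |

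**Adjusted power, by simulation.** 4,000 trials per setting, 376 per arm; age uniform 45 to 75, 51.5% men, BMI SD 4, 30% smokers (age shape, BMI and smoking assumed). Log-odds per 10 years / male / 5 BMI units / smoker were 0.20/0.40/0.10/0.20 (weak), 0.35/0.60/0.15/0.35 (middle) and 0.50/0.80/0.25/0.50 (strong).

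| Covariates | R² | Chi-square power | Adjusted power | Variance ratio of risk difference |
|---|---|---|---|---|
| Weak | 2.0% | 62.0% | 63.3% | 0.983 |
| Middle | 5.0% | 61.9% | 64.9% | 0.961 |
| Strong | 9.1% | 62.4% | 67.1% | 0.897 |

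Each simulated power has a Monte Carlo standard error of about √(0.62 × 0.38 / 4000) = 0.8 points. A separate simulation with one prognostic score and 1,500 runs gave 62.9% to 63.8%, 60.7% to 63.3% and 61.7% to 66.7% at R² of 2.1%, 5.4% and 10.9%.

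In patients, 752 × (1/0.983 − 1) = 13 and 752 × (1/0.897 − 1) = 86. The upper figure carries simulation noise: taking 1 − 0.091 = 0.909 as the ratio gives 752 × (1/0.909 − 1) = 75.

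**Proximal ADR** (37.9% to 45.9%, same 8 points assumed): 59.1% to 59.3%, 60.9% to 63.6% and 62.1% to 65.2%. Right ADR was not simulated; it is included by analogy.

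**SSL detection** (pilot 2.9% vs 5.7%): unadjusted power is 48.6%. Simulated power unadjusted and adjusted was 48.9% and 48.3%, 49.5% and 49.7%, and 48.1% and 46.9%, which is no gain. A score of the same strength explains under 2% of the variance of so rare an outcome.

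**Scale.** In the logistic model for ADR the SE of the log odds ratio rises with adjustment, from 0.151 to between 0.153 and 0.161. The narrower interval appears on the standardised risk difference, not on the odds ratio.

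**The case against.** The strongest reply is that nothing here is wrong. An unadjusted test of a randomized comparison is valid, and chance imbalance is already allowed for in its error rate. That stands: this is a matter of efficiency and consistency. The gain is also small, rests on an assumed R², and is close to nil for proximal ADR with weak covariates. The 8-point effect comes from another technique, and the water-exchange pilot showed no ADR increase. All of this stands too. The argument that APC and ADR could diverge is weakened because the t-test default may also yield an unadjusted APC comparison; the plan does not say which APC analysis is primary.

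A reader might infer that every secondary outcome loses precision. The documents do not support that:
- Right and proximal APC may already fall under the Poisson sentence.
- False positives are defined as AI identifications, and the AI runs only in AI-assisted procedures, so there is no meaningful comparison between arms.
- SSL detection gains nothing, and a model would rest on about 32 events (376 × 10/348 + 376 × 21/367 = 32.3).
- For non-neoplastic resections and procedure times, no gain has been calculated.

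A reader might also infer that the whole APC covariate list should be copied to ADR. Two of its six terms are unsuitable. CADe system may be undefined for controls unless it means the processor brand. Bowel preparation is graded at the procedure, and the documents do not say whether randomization comes before that.

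**Conclusion.** The point holds for overall, right and proximal ADR. The chi-square test is valid, but it leaves unused four baseline covariates that the plan needs anyway. If they explain 2% to 9% of ADR variance and ADR rises from 58.3% to 66.3%, adjustment cuts the variance of the risk difference by about 2% to 10% and raises power from about 62% to about 63% to 67% at 376 per arm. Both conditions are assumptions. The figures leave out any contribution from site, colonoscopist or indication, which the documents give no means of sizing. No gain is claimed for SSL detection or false positives. This is a modest improvement worth making because it is nearly free, not a correction of an error.

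**What to change.** Keep the Poisson sentence for APC as it stands, and add directly after it:

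> Overall, right and proximal ADR will be analysed by logistic regression on arm, age, sex, BMI and smoking history, together with the randomisation stratification factors (site or colonoscopist, and indication), reported as a standardised risk difference with 95% CI; the unadjusted chi-square result will be given as support. Right and proximal APC will use the same regression approach as overall APC.

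Do not carry CADe system or bowel preparation quality into the ADR model. Leave SSL detection unadjusted, and report false positives descriptively in the AI arm. The stratification factors belong in the ADR model because the Randomization section balances the arms on them.

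The cost is SAP wording and a few lines of code, with no new patients or visits. The four covariates are already required for APC, and the stratification factors are known at randomization. The text should be fixed before outcome data by arm are seen, so that the choice between adjusted and unadjusted ADR cannot depend on the result.

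### Neither planned APC analysis uses the randomisation strata, and the plan names neither the primary APC test nor a Poisson standard error that allows for overdispersion

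*Combined protocol and SAP*

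**What the plan says.** The Randomization section gives 1:1 allocation in blocks of four and states: "Stratification will be based on study sites, colonoscopists, and colonoscopy indications (primary screening, surveillance, and positive FIT or gFOBT").

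The Statistical analysis section contains two analyses that could test the primary outcome. Student's t-test "will be used for continuous variables and chi-square test will be used for categorical variables". Then "Poisson regression will be used to calculate incident rate ratios comparing the APC between the two arms". The covariate list given for that model reads: "adjusting for age, sex, body mass index, smoking history, CADe system, and bowel preparation quality". Site, colonoscopist and indication are not among these six covariates. The section does not say which analysis decides the APC hypothesis. It does not mention overdispersion, robust SEs or another count model.

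On the CADe covariate, the Artificial intelligence section says: "During AI-assisted procedures, the AI will be activated during the withdrawal phase of the procedure". No covariate value is stated for control patients. The Colonoscopy procedure section does say: "The study procedures employ standard high-definition colonoscopy video processors with integrated AI systems".

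The Introduction reports the pilot: "WE with AI demonstrated numerical APC enhancement (1.31 ± 1.80 vs. 1.14 ± 1.38"). Table 1 gives P = 0.152 for this comparison by Student's t-test.

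**The concern.** Two gaps interact.

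First, stratified blocking balances the arms on site, colonoscopist and indication, so the true variability of the arm comparison falls if these factors predict adenoma yield. An analysis that ignores them still charges that variation to error, and its SE is too wide.

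Second, an ordinary Poisson SE assumes that variance equals mean. Where adenoma counts vary more than that, the SE is too small and the test rejects too often.

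The errors run in opposite directions, and the SE type decides whether adding the strata has any effect. If SE type and primary test are chosen after the data are seen, that choice alone could move the result across 0.05.

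A smaller matter is that the CADe covariate needs a written value for controls, because some codings would make the arm coefficient unusable.

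**Working it through.** **1. The plan's own sample size.** Inputs from the Sample size calculation section: control APC 0.9, a 25% increase (to 1.125, difference 0.225), two-sided 5%, 80% power.
- Pure Poisson variance: n = (0.9 + 1.125) × (1.960 + 0.842)² / 0.225² = 314 per group, not 376.
- Two-means formula: n = 2 × SD² × (1.960 + 0.842)² / 0.225² gives 376 with SD = 1.10. No SD is stated. This value implies a variance about 1.2 times the mean (negative binomial dispersion about 0.19).

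**2. Pilot overdispersion.** Inputs from Table 1: control n = 348, mean 1.14, SD 1.38; AI n = 367, mean 1.31, SD 1.80.
- Variance/mean: 1.38²/1.14 = 1.67; 1.80²/1.31 = 2.47.
- Dispersion, (SD² − mean)/mean²: 0.59 and 1.12.
- Rate ratio: 1.31/1.14 = 1.149; log 0.1390.
- Ordinary SE: √[1/(348 × 1.14) + 1/(367 × 1.31)] = 0.0678; z = 2.05, P = 0.040, CI 1.01 to 1.31.
- Robust SE: √[1.38²/(348 × 1.14²) + 1.80²/(367 × 1.31²)] = 0.0967; z = 1.44, P = 0.151, CI 0.95 to 1.39.

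The robust result agrees with the reported t-test (P = 0.152).

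**3. Type I error with the ordinary SE.** Simulated at 376 per arm and APC 0.9, without strata or covariates: 6.9% at dispersion 0.19, 11.3% at 0.59, and 16.5% if 1.12 held in both arms. Robust SE and t-test stayed near 5% throughout.

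**4. Effect of the strata.** Simulation of 752 patients, 5,000 runs per scenario, blocks of four within colonoscopist by indication, control APC 0.9, rate ratio 1.25 (power) or 1.00 (type I error). Age, sex, BMI, smoking and preparation were in both models; CADe system and site were not simulated.

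Assumed, because the documents do not give them: 6 colonoscopists; indication mix 40:30:30; yield ratios 0.85:1:1.15 (mild), 0.75:0.95:1.3 (middle) or 0.6:0.9:1.5 (strong); colonoscopist log-SD 0, 0.2 or 0.4; covariate effects on the log rate of 0.02 per year of age, 0.4 for men, 0.08 per SD of BMI, 0.25 for smoking (25% smokers) and 0.05 per SD of preparation score; mean age 2 years apart between successive indications. Dispersion is 0.59 in both arms, except in the last row (0.59 control, 1.12 AI).

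Robust SE, without / with strata:

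| Scenario | SE of log rate ratio | Power, % | Type I error, % | Size-adjusted gain, points |
|---|---|---|---|---|
| Mild, 0 | 0.0895 / 0.0889 | 69.8 / 70.2 | 4.8 / 5.0 | −0.2 |
| Mild, 0.2 | 0.0895 / 0.0878 | 70.1 / 71.7 | 4.9 / 5.2 | +0.7 |
| Middle, 0.2 | 0.0892 / 0.0862 | 70.4 / 72.9 | 4.5 / 5.4 | −0.1 |
| Strong, 0 | 0.0886 / 0.0837 | 71.5 / 75.7 | 3.9 / 4.8 | +1.3 |
| Strong, 0.2 | 0.0887 / 0.0824 | 74.8 / 79.1 | 4.2 / 5.4 | +1.0 |
| Strong, 0.4 | 0.0892 / 0.0789 | 71.7 / 80.4 | 3.2 / 5.0 | +2.8 |
| Middle, 0.2, AI dispersion 1.12 | 0.0967 / 0.0939 | 63.8 / 65.7 | 5.1 / 5.7 | +0.1 |

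Monte Carlo SE is about 0.6 point for power and 0.3 point for type I error. The last column sets each test to 5% by a normal approximation: adjusted power = Φ(z_power + z_(1−α/2) − 1.96), with α the simulated type I error.

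A separate simulation of 1,500 runs compared the actual spread of the log rate ratio without / with strata: 0.0896 / 0.0895 (middle) and 0.0843 / 0.0842 (strong). Blocking has already delivered the precision; adding the strata corrects the reported SE.

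The t-test behaves in the same way: type I error 2.8% to 4.7%, and a linear model with strata adds 0.8 to 7.8 points of power. With the ordinary Poisson SE the strata change almost nothing: SE 0.0733 without and 0.0734 to 0.0735 with; type I error 6.6% to 12.3% without and 6.5% to 12.0% with. The mean rate ratio is about 1.25 either way.

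**5. CADe coding.** Intercept, arm and brand in both arms: rank 3 of 3. Intercept, arm and separate CAD-EYE and Endo-AID indicators, both zero in controls: rank 3 of 4, so the arm effect is not estimable. One brand indicator set to zero in all controls makes the arm coefficient the other brand's effect.

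**The case against.** **The t-test may be the intended primary test.** The plan introduces the Poisson model to estimate rate ratios, and the pilot tested APC by t-test. On that reading the inflated Poisson error does not govern the primary conclusion. This is a fair, perhaps natural, reading, but it is unwritten. A reader might infer that the primary test is anti-conservative; the documents support only that it would be if the Poisson model with ordinary SEs were used.

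**The power gain from the strata is mostly recalibration.** This stands. Size-adjusted gains run from −0.2 to +2.8 points, and the actual spread of the estimate does not change. The largest nominal gain also needs strong assumed heterogeneity. One row is out of line: at strong, 0.2, the SE of 0.0887 implies power near Φ(0.2231/0.0887 − 1.96) = 71%, against 74.8% simulated. Neither end of the range of gains depends on it.

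**The simulation omits CADe system.** This stands. If platform tracks site or colonoscopist, the planned model already absorbs some stratum variation. The documents do not say whether it does.

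**The failing CADe codings are hypothetical.** This stands. Processors with integrated AI make platform in both arms the sensible reading. A reader might infer that the planned model cannot estimate the arm effect, but nothing in the plan specifies a coding that would cause this.

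**Other methods would serve.** Negative binomial, quasi-Poisson or a linear model with strata would also do. What matters is that one is named in advance.

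**Conclusion.** The concern holds as a specification gap in the primary analysis. The omission of the strata, the unnamed primary test and the unstated SE can be read directly from the plan. The pilot's own figures show that SE type alone can change the conclusion. An ordinary Poisson SE would give a type I error of about 7% to 12% over the dispersions in the stratified simulation, and about 7% even at the dispersion implied by 376 per group.

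Omitting the strata is the milder fault. It does not bias the rate ratio, and with a t-test or robust SE it makes the test mildly conservative (about 3% to 5%). The nominal power gain from adding them is 0.4 to 8.7 points, and 2.5 points or less in four of seven scenarios. Its size rests wholly on assumed heterogeneity, and nearly all of it comes from the test returning to nominal size.

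A reader might also infer that true power is only 66% to 80%. That range assumes that pilot dispersion applies at an APC of 0.9. At SD 1.10, the value that reproduces 376, power is about 80%. The documents do not settle which dispersion applies.

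**What to change.** State that the primary APC comparison is a Poisson model with robust (sandwich) SEs. It should include arm, indication (three levels), colonoscopist, and age, sex, BMI, smoking and bowel preparation quality as planned. Add site if colonoscopists are not nested within it, and give a rule for pooling colonoscopists with few patients. The strata and the robust SE should be specified together, since strata without it change almost nothing. Label the t-test on APC supportive. State how missing covariates are handled, so that the model keeps the intention-to-treat population.

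As a clarification, define the CADe covariate as the processor platform (Fujifilm or Olympus) recorded for every patient in both arms, or drop it if it is redundant with colonoscopist. Any brand comparison should be an arm-by-platform interaction, labelled exploratory.

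The cost is a few sentences and at most one worksheet column; the strata are already held from randomisation. The software sentence, "All statistical analyses will be performed using Python version 3.10 (SciPy Library"), should also name the regression package. SciPy 1.17.1 has no Poisson regression routine, although that release needs Python 3.11 or later and so is not the plan's version. A package such as statsmodels offers robust SEs as an option.

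The downside is that, at pilot dispersion, the robust SE with strata is 0.079 to 0.094 against about 0.073 for the ordinary one. Power at 752 patients then reads about 66% to 80% instead of 80% to 85%. At SD 1.10 it reads about 80%.

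### The Poisson model for APC adjusts for a bowel preparation score that the plan does not secure as a pre-randomisation or blinded measurement

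*Combined protocol and SAP*

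**What the plan says.** Study outcomes: "The primary outcome is APC, calculated as the total number of adenomas detected divided by the total number of colonoscopies performed".

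Statistical analysis: "Poisson regression will be used to calculate incident rate ratios comparing the APC between the two arms", and the model is fitted "adjusting for age, sex, body mass index, smoking history, CADe system, and bowel preparation quality". The same section says that Student's *t* "test will be used for continuous variables and chi-square test will be used for categorical variables". It does not say which of these is the primary test of APC.

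Colonoscopy procedure: "Bowel preparation regimens will align with established standard practices at each individual site". Preparation quality is to "be carried out using the Boston Bowel Preparation Scale scoring system". The text does not say who grades, at what point in the examination, or whether that person knows the arm. In both arms "insertion and withdrawal of the colonoscope will be executed by the same colonoscopist".

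Artificial intelligence: the detection system is switched on only for withdrawal and draws boxes that the operator sees. Data collection: the investigators and their teams complete the study worksheet. No section describes blinding, and Randomization does not say when allocation takes place or becomes known relative to preparation, insertion or grading.

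**The concern.** Age, sex, body mass index and smoking history are settled before a patient is randomised, so adjusting for them cannot introduce a systematic difference between arms. The Boston score is a different kind of variable. It describes what is seen during the procedure, after some cleaning has been done, and nothing in the plan places it before allocation or AI activation, or gives it to someone unaware of the arm.

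Two routes could make the recorded score depend on the arm. The first is grading: if it is done during or after withdrawal by someone who has watched the AI output, the impression of cleanliness may shift. The second is cleaning. An operator who knows the arm may clean differently, and on withdrawal the areas flagged by AI are re-examined, which happens in one arm only. Both are inferences; the documents neither report them nor rule them out.

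If either route operates, conditioning on the score moves the APC rate ratio. With differential grading, the model corrects for a difference in cleanliness that does not exist. With differential cleaning, it removes part of what allocation actually caused. In both cases the adjusted estimate departs from the effect that randomisation protects.

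**Working it through.** **The plan's own figures.** The inputs under Sample size calculation are a control APC of 0.9, a 25% relative increase (to 1.125, a difference of 0.225 and a rate ratio of 1.25), two-sided 5%, 80% power and 10% dropout. No SD is stated.

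- Two means: n = 2(1.96 + 0.842)² SD² / 0.225². This gives 376 per group with an assumed SD of 1.1 (the SD implied by 376 is 1.101).
- Poisson, log scale: n = (1.96 + 0.842)² (1/0.9 + 1/1.125) / (ln 1.25)² = 315.3, so 316 per group. This does not give 376.
- Dropout: 752 / 0.9 = 835.6, so 836, as stated.

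No covariate enters these figures, so removing one leaves 376, 752 and 836 unchanged.

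**Bias by formula.** Let r be the rate ratio for APC per score point and d the systematic arm difference in score (AI minus control). The adjusted rate ratio is then approximately 1.25 × r^(−d), and the bias on the log scale is −d ln r. The documents give neither r nor d; the values below are assumptions.

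| r | d (points) | AI arm scores higher | AI arm scores lower | ǀd ln rǀ / ln 1.25 |
|---|---|---|---|---|
| 1.05 | 0.2 | 1.238 | 1.262 | 4% |
| 1.10 | 0.2 | 1.226 | 1.274 | 9% |
| 1.05 | 0.5 | 1.220 | 1.281 | 11% |
| 1.10 | 0.5 | 1.192 | 1.311 | 21% |

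With d = 0 the factor is 1 and there is no bias.

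**Simulation check.** Poisson counts were generated with control APC 0.9. Further assumptions, none from the documents: true score SD 1.2, scoring error SD 0.6, log-APC slope 0.05, 0.10 or 0.20 per point, and an arm difference in the recorded score that does not reflect true cleanliness. Bias was read from 400,000 patients per arm, and error rates from 1,500 trials of 376 per arm.

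| Slope | Adjusted IRR, true 1.25, d = +0.25 / −0.25 | Adjusted IRR, true 1.25, d = +0.5 / −0.5 | Type I error with score, d = +0.5 / −0.5 | Type I error without score, same scenarios |
|---|---|---|---|---|
| 0.05 | 1.238 / 1.267 | 1.229 / 1.275 | 5.7% / 5.7% | 4.7% / 5.0% |
| 0.10 | 1.222 / 1.283 | 1.201 / 1.295 | 8.9% / 9.5% | 6.1% / 6.0% |
| 0.20 | 1.203 / 1.300 | 1.154 / 1.355 | 16.0% / 16.9% | 5.9% / 6.5% |

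Without the score, the simulated rate ratio stayed at 1.244–1.257 for a true 1.25 and 0.996–1.003 for a true 1.00. With the score and d = 0, it was 1.245–1.250 and 0.997–1.003.

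The Monte Carlo standard error of a 5% rejection rate is √(0.05 × 0.95 / 1,500) = 0.56 points, so 5.7% is not distinguishable from nominal. A slope of 0.20 means e^0.20 = 1.22, or 22% per point. That row is a stress case outside the 5–10% range.

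**The case against.** The case on the other side is substantial, and most of it limits how far the point can be taken.

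- A reader might infer that the primary analysis is compromised. The plan does not name the Poisson model as primary, and 376 per group fits a comparison of two means (assumed SD 1.1) rather than a Poisson calculation. If the *t*-test is primary, that comparison carries no covariate and only the adjusted rate ratio is exposed.
- A reader might infer that the colonoscopist grades the score knowing the arm. That is plausible, but the quoted sentence on the colonoscopist concerns who handles the instrument. The grader and time point are simply not stated.
- A reader might infer that preparation quality arises after allocation. The oral preparation may precede randomisation, and no regimen is specific to an arm.
- The Introduction's statement that "Water Exchange (WE) colonoscopy maximizes bowel cleanliness during insertion" belongs to a contrast with air insufflation. Both arms here use water exchange, under the same technique check at the cecum and the same minimum clean withdrawal time. It is no evidence of a difference between arms.
- Chance imbalance in true cleanliness is not bias, and adjusting for it is the ordinary reason to include a prognostic covariate.
- With an assumed score SD of 1.2, the standard error of the arm difference is 1.2 × √(2/376) = 0.09. A gap of 0.2–0.5 points is therefore about 2 to 6 standard errors, a pronounced effect that a table by arm would probably reveal.

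All of this stands as a limit on size and certainty. It does not remove the point: this is the only model the plan ties to APC by name, and nothing in the plan excludes grading or cleaning that depends on the arm.

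**Conclusion.** The concern holds as an avoidable risk of bias in the adjusted APC rate ratio. It is not a demonstrated bias, and the documents do not support calling it a flaw in the primary test. It requires a systematic effect of arm on the recorded score, through grading or cleaning, and the documents describe no direct route from AI to cleanliness. With no such effect the bias is zero.

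The size is unknown because there are no score data. On the assumed range (0.2–0.5 points, 5–10% per point), the shift is 4–21% of the targeted log effect, in either direction. If the recorded score differs by 0.5 points without a real difference in cleanliness, the simulated type I error is near nominal at a slope of 0.05 and about 9% at 0.10. Modest is the fair description. The case for acting is that the remedy is cheap.

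**What to change.** In the Statistical analysis section:

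1. State that the main Poisson model for APC adjusts only for covariates fixed before randomisation, with the stratification factors (site, colonoscopist, indication) among them. None of the three is in the present list. Leave bowel preparation quality out. CADe system may stay if it is defined in both arms by equipment settled before allocation.
2. Report the Boston score by arm.
3. Keep the score-adjusted model as a labelled sensitivity analysis.

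It would also help to state in Colonoscopy procedure who grades the score, when, and with what knowledge of the arm, so that the sensitivity analysis can be interpreted.

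The cost is SAP wording. The sample size is unaffected. The downside is a small loss of precision if cleanliness strongly predicts APC. In the simulation with no arm difference, dropping the score lowered power by at most 0.6 percentage points (87.1% to 86.6%, 85.1% to 84.9% and 84.9% to 84.3% for slopes 0.05, 0.10 and 0.20).
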